5.13.1 NKTR-214 Dose-Delay and Reduction Criteria

Dose delays and reductions are permitted for NKTR-214. NKTR-214 may be delayed or reduced to 0.003 mg/kg based on observed drug-related toxicities. If the NKTR-214 dose is reduced to 0.003 mg/kg, the dose level should remain at this level throughout the remainder of the study.

NKTR-214 should be delayed for the following reasons:

- For persistent Grade 2 related toxicity, a dose delay or dose reduction may be implemented at the discretion of the Investigator.
 - Grade \geq 2 creatinine increase
 - For patients who must delay study treatment due to Grade \geq 2 creatinine increase due to a non-inflammatory cause, delay retreatment with study drug for approximately 3 to 5 days. After the dosing delay, the patient may resume study drug when serum creatinine has returned to Grade \leq 1, as assessed within 24 hours prior to redosing. For further guidance, refer to renal adverse event management algorithm in current Nivolumab Investigator's Brochure.
- Grade \geq 3 toxicity at least possibly related to NKTR-214: NKTR-214 must be delayed until resolution to Grade 1 or baseline (unless otherwise requiring permanent discontinuation, per Section 5.14.1.1) with the following exceptions:
 - Grade \geq 3 lymphopenia
 - Grade \geq 3 asymptomatic amylase or lipase elevation
- Patient has acute infection (e.g., fever, upper or lower respiratory tract infection) requiring systemic antibiotic therapy. Patient may resume study treatment once free of signs or symptoms for 72 hours after completion of antibiotic therapy (See Section 5.13.7).
- Any adverse event, laboratory abnormality, or intercurrent illness which, in the judgment of the Investigator, warrants delaying the dose of study medication.

NKTR-214 dosing may resume at the same dose or at a lower dose level when toxicity resolves to Grade 1 or returns to baseline, except for instances where the potential recurrence of the event poses an undue risk for the patient. Medical Monitor consultation is required for dose reduction.

5.13.2 Nivolumab Dose-Delay and Reduction Criteria

Dose reductions for nivolumab are not permitted in this study.

Nivolumab administration should be delayed for the following:

- Grade 2 non-skin, drug-related AE, with the exception of fatigue
- Grade 2 drug-related creatinine, AST, ALT and/or total bilirubin abnormalities

- Grade 3 skin, drug-related AE
- Grade 3 drug-related laboratory abnormality, with the following exceptions:
 - Grade 3 lymphopenia or asymptomatic amylase or lipase does not require dose delay
 - Grade ≥ 3 AST, ALT, and/or total bilirubin will require dose discontinuation (unless satisfying the Cycle 1 ALT/AST elevation criteria outlined in Section 5.13.3)
- Patient has acute infection (e.g., fever, upper or lower respiratory tract infection) requiring systemic antibiotic therapy. Patient may resume study treatment once free of signs or symptoms for 72 hours after completion of antibiotic therapy (See Section 5.13.7).
- Any adverse event, laboratory abnormality, or intercurrent illness which, in the judgment of the Investigator, warrants delaying the dose of study medication.

Patients who require delay of nivolumab should be re-evaluated weekly or more frequently if clinically indicated and resume nivolumab dosing when retreatment criteria are met.

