5.13 Dosage Modification

Every effort should be made to follow planned dosing schedules for all study drugs in both treatment arms. Study drug administration may be delayed or modified for toxicity as described below and must be discontinued as required by criteria described in Section 5.14.

Dose modification for NKTR-214 and nivolumab in Arm A may be considered independently based on Investigator assessment of relationship of a toxicity to each of the study drugs. If only one of the study drugs meets the criteria for dose delay, then administration of the other study drug may be continued or delayed at the discretion of the Investigator. Likewise, in the event that one of the study drugs in Arm A is permanently discontinued due to toxicities, the other can continue to be administered.

Patients who require delay of nivolumab or NKTR-214 should be re-evaluated weekly or more frequently if clinically indicated and should resume treatment with combination of NKTR-214 and nivolumab when retreatment criteria are met (Section 5.13.7). Immuno-oncology agents are associated with AEs that can differ in severity and duration from AEs caused by other therapeutic classes. NKTR-214 and nivolumab are considered an immuno-oncology agent in this protocol. Early recognition and management of AEs associated with immuno-oncology agents may mitigate severe toxicity.

For patients randomized to Arm A: NKTR-214 or nivolumab administration defines a scheduled nominal dosing visit (i.e., Cycle X Day 1, Cycle X Day 22). If a patient is assessed for an intended nominal dosing visit but study drug is not administered (e.g., due to an AE requiring dose delay, drug unavailable), any assessments performed during that visit should be recorded as “unscheduled.” When study drug administration resumes, all assessments should be performed as scheduled for the next nominal dosing visit (i.e., Cycle X Day 1 or Cycle X Day 22 Visit).

For patients randomized to Arm B: Cycle 1 Day 1 is defined by the date that the first dose of sunitinib or cabozantinib is administered. Within a cycle, missed doses of sunitinib should be skipped and not replaced. Scheduled Cycle X Day 1 and Cycle X Day 22 visits are fixed relative to Cycle 1 Day 1, regardless of dose delays. If drug dosing is delayed at the time of these scheduled visits (e.g., due to an AE requiring dose delay, drug unavailable), the cycle visit is not shifted and all assessments should be performed as scheduled.

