5.13.3 Dose-Modification Criteria for NKTR-214 and Nivolumab for Cycle 1 ALT/AST Elevations

These recommendations are for Cycle 1 only and are not intended to serve as rigid guidelines or to replace clinical judgment. Subsequent cycles should follow standard Hepatic Adverse Event Management Algorithm (see the nivolumab Investigator's Brochure).

Rule out non-inflammatory etiologies. If non-inflammatory cause, treat accordingly and continue NKTR-214 and nivolumab. Consider imaging for obstruction.

If during monitoring ALT/AST increases, follow the guidance for the highest levels.

ALT or AST > 3.0 to \leq 5.0 \times ULN (within first cycle of NKTR-214 + nivolumab)

Increase frequency of liver function test (LFT) monitoring to approximately every 3 days and delay treatment until lab abnormalities resolve to Grade 1 or baseline.

If no improvement within 7 days, treat with 0.5-1 mg/kg/day prednisone equivalents, and taper steroids over at least 1 month before resuming treatment.

ALT or AST > 5.0 to \leq 8.0 \times ULN (within first cycle of NKTR-214 + nivolumab)

Increase frequency of monitoring to approximately every 3 days until lab abnormalities resolve to Grade 1 or baseline.

Treatment must be delayed until lab abnormalities resolve to Grade 1 or baseline.

If no improvement within 7 days (follow Hepatic Adverse Event Management Algorithm);

- Discontinue NKTR-214 + nivolumab
- 1 to 2 mg/kg/day prednisone equivalents followed by corticosteroid taper over at least one month
- Consult gastroenterologist
- Consider adding non-corticosteroid immunosuppressive medication if no improvement in > 3-5 days, worsens or rebounds while on steroids

ALT or AST > 8.0 × ULN (follow Hepatic Adverse Event Management Algorithm)

- Discontinue NKTR-214 + nivolumab
- Increase frequency of monitoring to approximately 1-2 days
- 1 to 2 mg/kg/day prednisone equivalents followed by corticosteroid taper over at least one month
- Consult gastroenterologist
- If no improvement in > 3–5 days, worsens or rebounds, add non-corticosteroid immunosuppressive medication

Please refer to Section 5.14 for discontinuation criteria.

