5.14.1.1 NKTR-214 Combined with Nivolumab Discontinuation Criteria

Patients meeting any of the following criteria will be required to permanently discontinue all assigned study drug(s). However, per Investigator assessment, NKTR-214 or nivolumab may be

continued as a monotherapy if the toxicities listed below are considered related to only one of the study drugs, once the criteria to resume are met (Section 5.13.7). For CVA events and suspected TIA events, follow the criteria described below (additional details are provided in the CVA management algorithm in [Appendix 6](#)).

NKTR-214 combined with nivolumab treatment should be permanently discontinued for the following:

- Any \geq Grade 2 drug-related uveitis, eye pain or blurred vision that does not respond to topical therapy and does not improve to Grade 1 severity within the retreatment period OR requires systemic treatment
- Grade 3 or 4 infusion reaction of any duration that occurs during the:
 - NKTR-214 infusion or prior to the nivolumab infusion requires discontinuation of NKTR-214.
 - Nivolumab infusion or later requires discontinuation of both NKTR-214 and nivolumab.
- Any Grade 3 non-skin, drug-related AE lasting > 7 days or recurs, with the following exceptions for laboratory abnormalities, drug-related uveitis, pneumonitis, bronchospasm, neurologic toxicity, hypersensitivity reactions, and endocrinopathies
 - Grade 3 drug-related uveitis, pneumonitis, bronchospasm, neurologic toxicity, myocarditis, or hypersensitivity reaction of any duration requires discontinuation
 - Grade 3 drug-related endocrinopathies (excluding adrenal insufficiency) adequately controlled with only physiologic hormone replacement do not require discontinuation.
 - Note: For adrenal insufficiency of Grade ≥ 3 , treatment needs to be discontinued regardless of control with hormone replacement (hospitalization for diagnostic workup of adrenal insufficiency without severe symptoms should not require discontinuation).
 - Grade 3 drug-related laboratory abnormalities do not require treatment discontinuation except:
 - Grade 3 drug-related thrombocytopenia > 7 days or associated with bleeding requires discontinuation
 - Any drug-related LFT abnormality that meets the following criteria require discontinuation (also see Hepatic Adverse Event Management Algorithm, in nivolumab Investigator's Brochure):

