 - ◆ Treatment-emergent ALT or AST > 3 times ULN ($> 2 \times$ baseline AND $> 3 \times$ ULN for patients with baseline elevation) AND
 - ◆ Total bilirubin > 2 times ULN ($> 2 \times$ baseline AND $> 2 \times$ ULN for patients with baseline elevation) or clinical jaundice, without initial findings of cholestasis (e.g., elevated serum alkaline phosphatase) (see Section 8.10)

In most cases of Grade 3 AST or ALT elevation that do not improve with hepatic AE management, study treatment will be permanently discontinued (see Section 5.13 for more details). If the Investigator determines a possible favorable benefit/risk ratio that warrants continuation of study treatment, a discussion between the Investigator and the Medical Monitor must occur. For IL-2 mediated ALT/AST elevations $< 8.0 \times \text{ULN}$ in Cycle 1 only, study treatment does not need to be discontinued.

- Any Grade 4 drug-related adverse event or laboratory abnormality (including but not limited to creatinine, AST, ALT, or total bilirubin), except for the following events which do not require discontinuation:
 - Grade 4 neutropenia ≤ 7 days
 - Grade 4 lymphopenia or leukopenia or asymptomatic amylase or lipase
 - Isolated Grade 4 electrolyte imbalances/abnormalities that are not associated with clinical sequelae and are corrected with supplementation/appropriate management within 72 hours of their onset
 - Grade 4 drug-related endocrinopathy adverse events (except adrenal insufficiency or hypophysitis), such as, hyper- or hypothyroidism, or glucose intolerance, which resolve or are adequately controlled with physiologic hormone replacement (corticosteroids, thyroid hormones) or glucose-controlling agents, respectively, may not require discontinuation after discussion with and approval from the Medical Monitor.
 - Note: For Grade ≥ 3 adrenal insufficiency and/or Grade ≥ 4 hypophysitis, treatment needs to be discontinued regardless of control with hormone replacement (hospitalization for diagnostic workup of adrenal insufficiency without severe symptoms should not require discontinuation).
- Any event that leads to delay in dosing lasting > 8 weeks from the previous dose requires discontinuation, with the following exceptions:

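### For an improving isolated Grade 3 AST/ALT after Cycle 1, or an isolated Grade 3 bilirubin in any cycle, Protocol 5.13.2 requires nivolumab to stop, 5.14.1.1 does not, and neither section is given precedence

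*Protocol*

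**What the plan says.** Section 5.13.2 sets the delay rules for nivolumab. Under its bullet on Grade 3 drug-related laboratory results, it says that Grade 3 or higher "AST, ALT, and/or total bilirubin will require dose discontinuation (unless satisfying the Cycle 1 ALT/AST elevation criteria" of Section 5.13.3). The carve-out is for Cycle 1 only. The thresholds in 5.13.3 are for ALT and AST, and none is given for bilirubin. For later cycles 5.13.3 says: "Subsequent cycles should follow standard Hepatic Adverse Event Management Algorithm". That algorithm is in the nivolumab Investigator's Brochure, which is not among the documents.

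Section 5.14.1.1 sets the permanent discontinuation criteria for Arm A. Its general rule is that "Grade 3 drug-related laboratory abnormalities do not require treatment discontinuation except" in listed situations. The listed liver exception begins "Any drug-related LFT abnormality that meets the following criteria require discontinuation". Those criteria need both limbs: ALT or AST above 3 x ULN, and total bilirubin above 2 x ULN or clinical jaundice, without initial signs of cholestasis. The section then adds: "In most cases of Grade 3 AST or ALT elevation that do not improve with hepatic AE management, study treatment will be permanently discontinued". If the investigator sees grounds to continue, a discussion with the Medical Monitor is mandatory.

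The cross-references run in both directions. The opening of 5.13 says that study drug "must be discontinued as required by criteria described in Section 5.14", and 5.13.3 ends with "Please refer to Section 5.14 for discontinuation criteria". In the other direction, the Grade 3 AST/ALT sentence of 5.14.1.1 says that treatment "will be permanently discontinued (see Section 5.13 for more details").

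**The concern.** A patient on Arm A can have a Grade 3 liver result for which one section makes stopping nivolumab mandatory and the other does not. An investigator who reads only 5.14.1.1, together with the resume rules in 5.13.7, could delay nivolumab, wait for recovery and restart it. That would be a deviation from the nivolumab-specific rule in 5.13.2. An investigator who reads 5.13.2 would end nivolumab for a patient whom 5.14.1.1 might have kept on treatment.

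The cases are foreseeable. Section 5.13.4 names raised transaminases as a toxicity shared by the two Arm A drugs. It says that elevations from NKTR-214 occur mainly in Cycles 1 and 2, while the carve-out ends with Cycle 1. It also says that higher-grade liver abnormalities with nivolumab tend to come later. What is at stake is the consistency of a safety rule across sites and the handling of deviations.

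**Working it through.** The check is a case-by-case comparison. All cases are drug-related. Isolated means that the other limb of the combined criterion in 5.14.1.1 is not met: for AST/ALT, no bilirubin above 2 x ULN and no jaundice; for bilirubin, no ALT or AST above 3 x ULN.

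| Case | 5.13.2 (nivolumab) | 5.14.1.1 | Same answer? |
|---|---|---|---|
| Isolated Grade 3 AST/ALT, Cycle 2 on, improving | Stop | Stop not required | No |
| Isolated Grade 3 AST/ALT, Cycle 2 on, not improving | Stop | Stop in most cases; continuing calls for a Medical Monitor discussion | Mostly |
| Isolated Grade 3 bilirubin, any cycle | Stop (the carve-out covers ALT/AST only) | Stop not required (not a listed exception) | No |
| Cycle 1 ALT/AST > 5 to 8 x ULN, improving | Delay, through 5.13.3 | Stop not required | Yes |
| Grade 3 AST/ALT from Cycle 2 on, with bilirubin > 2 x ULN, no cholestasis | Stop | Stop | Yes |
| Grade 4 AST, ALT or bilirubin | Stop | Stop | Yes |

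So there are two clear mismatches, rows 1 and 3, and a small residual one in row 2.

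**Is precedence stated?** No sentence in 5.13 or 5.14 says which section prevails. The indirect evidence is as follows.

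- Toward 5.14.1.1: the opening of 5.13, the end of 5.13.3, the NKTR-214 delay rule in 5.13.1 (which defers to 5.14.1.1 for permanent stops), and several mentions in 5.13.7, including its bar on resuming, which cites 5.14.1.1 and not 5.13.2.
- Toward 5.13.2: its liver bullet is a mandatory rule with its own exception and, unlike 5.13.1, does not defer to 5.14.1.1. Section 5.14.1.1 sends Grade 3 AST/ALT back to 5.13. The liver bullet among the resume rules of 5.13.7 covers Grade 2 only, which fits a stop at Grade 3.
- The back-reference concerns AST/ALT only, so for isolated bilirubin the lean toward 5.14.1.1 is clearer, though still not explicit.

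**Does the Cycle 1 carve-out cover the expected timing?** Section 5.13.4 gives a median onset of 3.3 months for higher-grade nivolumab liver abnormalities. At 30.4 days per month, 3.3 x 30.4 = about day 100. A cycle is 42 days, so Cycle 3 runs from day 2 x 42 + 1 = 85 to day 3 x 42 = 126. The median therefore falls in nominal Cycle 3, after the carve-out has ended.

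**The case against.** The strongest reply is that there is no true contradiction. Section 5.14.1.1 says a stop is not required; it does not order treatment to continue. A site can meet both sections by stopping nivolumab. That stands, and a reader who infers that the sections give orders that cannot both be obeyed goes too far. What remains is that a site relying on 5.14.1.1 to continue breaches 5.13.2.

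A second reply is a split by scope: 5.13.2 governs nivolumab, and 5.14.1.1 governs stopping both drugs. This does not hold. Section 5.14.1.1 also says when one drug may continue alone, and one of its last criteria concerns continued nivolumab dosing specifically.

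Third, for Grade 3 AST/ALT that does not improve, the mandatory Medical Monitor discussion is a central check on continuation. That stands for those cases. Nothing comparable is written for isolated bilirubin.

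Fourth, from Cycle 2 the Brochure algorithm may settle practice for AST/ALT. It may, but it cannot be seen here, and two protocol sentences would still disagree.

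Two further inferences are tempting and not supported. One is to count the doses between the median onset and the two-year limit as the difference between the rules. The looser rule itself requires a delay until recovery and, where steroids were used, a completed taper, so that count would describe an extreme patient. The other is to treat the Cycle 1 wording as a conflict of the same weight. Section 5.13.3 stops both drugs for ALT/AST above 5 and up to 8 x ULN without improvement in 7 days, while 5.14.1.1 exempts IL-2 mediated elevations below 8.0 x ULN with no such condition. But 5.13.3 describes itself as guidance rather than fixed rules, and the 7-day step can be read as separating transient IL-2 effects from immune-mediated hepatitis.

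**Conclusion.** The inconsistency is real but narrow. For an improving isolated Grade 3 AST/ALT from Cycle 2 on, and for an isolated Grade 3 bilirubin in any cycle, 5.13.2 makes stopping nivolumab mandatory and 5.14.1.1 does not. The pointers lean toward 5.14.1.1 without settling the matter. The importance is that of a minor to moderate clarification.

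The size cannot be put in patients or doses, because the documents do not give the frequency of these cases. The documents do not support a claim that Arm A dosing will in fact be uneven, or that any efficacy comparison is affected; no alpha, power or primary test depends on the rule. Nor do they show which rule is medically right. The conclusion rests on reading the liver bullet of 5.13.2 as limited to drug-related results, like the bullet it sits under, and on the Brochure algorithm being unavailable.

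**What to change.** Check the hepatic algorithm in the nivolumab Investigator's Brochure first. Then state one rule in both sections, in one of two ways.

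- **Stricter rule.** Add isolated Grade 3 AST/ALT after Cycle 1, and isolated Grade 3 bilirubin in any cycle, to the exceptions in 5.14.1.1 as a stop for nivolumab. Reconcile the sentences on non-improving AST/ALT and on the Medical Monitor discussion with it. The bar on resuming in 5.13.7 already cites 5.14.1.1 and can stay.
- **Looser rule.** Change the liver bullet of 5.13.2 to: delay; discontinue per 5.14.1.1. Extend the return-to-baseline bullet of 5.13.7 from Grade 2 to Grades 2-3.

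Until this is settled, tell sites to follow the stricter 5.13.2 rule for nivolumab; doing so meets both sections.

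As optional tidying, align the Cycle 1 sentence of 5.14.1.1 with 5.13.3 on the 7-day condition and on whether the upper limit is below 8.0 or up to and including 8.0 x ULN.

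The cost is a protocol clarification or amendment and a notice to sites. Sample size, alpha and the analyses do not change.

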5.13.3 Dose-Modification Criteria for NKTR-214 and Nivolumab for Cycle 1 ALT/AST Elevations

These recommendations are for Cycle 1 only and are not intended to serve as rigid guidelines or to replace clinical judgment. Subsequent cycles should follow standard Hepatic Adverse Event Management Algorithm (see the nivolumab Investigator's Brochure).

Rule out non-inflammatory etiologies. If non-inflammatory cause, treat accordingly and continue NKTR-214 and nivolumab. Consider imaging for obstruction.

If during monitoring ALT/AST increases, follow the guidance for the highest levels.

ALT or AST > 3.0 to \leq 5.0 \times ULN (within first cycle of NKTR-214 + nivolumab)

Increase frequency of liver function test (LFT) monitoring to approximately every 3 days and delay treatment until lab abnormalities resolve to Grade 1 or baseline.

If no improvement within 7 days, treat with 0.5-1 mg/kg/day prednisone equivalents, and taper steroids over at least 1 month before resuming treatment.

ALT or AST > 5.0 to \leq 8.0 \times ULN (within first cycle of NKTR-214 + nivolumab)

Increase frequency of monitoring to approximately every 3 days until lab abnormalities resolve to Grade 1 or baseline.

Treatment must be delayed until lab abnormalities resolve to Grade 1 or baseline.

If no improvement within 7 days (follow Hepatic Adverse Event Management Algorithm);

- Discontinue NKTR-214 + nivolumab
- 1 to 2 mg/kg/day prednisone equivalents followed by corticosteroid taper over at least one month
- Consult gastroenterologist
- Consider adding non-corticosteroid immunosuppressive medication if no improvement in > 3-5 days, worsens or rebounds while on steroids

ALT or AST > 8.0 × ULN (follow Hepatic Adverse Event Management Algorithm)

- Discontinue NKTR-214 + nivolumab
- Increase frequency of monitoring to approximately 1-2 days
- 1 to 2 mg/kg/day prednisone equivalents followed by corticosteroid taper over at least one month
- Consult gastroenterologist
- If no improvement in > 3–5 days, worsens or rebounds, add non-corticosteroid immunosuppressive medication

Please refer to Section 5.14 for discontinuation criteria.

5.13.4 Monitoring and Management of Elevated Hepatic Transaminases

Elevated hepatic transaminases are an overlapping toxicity that can occur for both NKTR-214 and nivolumab. The elevations in hepatic transaminases associated with NKTR-214 typically occur at the time of peak active cytokine concentration in the blood (Days 4-8) and are often accompanied by other IL-2 mediated AEs such as flu-like symptoms, rash or pruritus. The transient elevations in hepatic transaminases are usually asymptomatic, mild or moderate in severity, not associated with increased total bilirubin and alkaline phosphatase, resolve spontaneously without treatment, and predominantly occur in Cycle 1 and Cycle 2; the transaminase elevations are considered to occur in the context of IL-2 mediated AEs. For transaminase elevations occurring in Cycle 1 consistent with a cytokine-related effect without alternative etiologies, follow the Cycle 1 hepatic adverse event management guideline (Section 5.13.3).

Hepatic events, including elevated LFTs, have also been observed for nivolumab. Most cases were of low or moderate severity. Higher grade abnormalities are concerning for immune-mediated hepatitis, and typically occur with a later onset (median time to onset of 3.3 months). Immune-mediated hepatitis generally results in a quick rise in LFTs and responds to corticosteroids or immune-modulating agents. For transaminase elevations occurring in Cycle 2 onwards potentially involving an immune-mediated mechanism, follow the immune-mediated hepatic adverse event management guidelines in the nivolumab Investigator's Brochure or product labeling for appropriate management.

